16.2 DERIVED EFFICACY VARIABLES

The efficacy variables are derived as follows:

- *CDRS-R responders* are defined as patients with a $\geq 40\%$ reduction from baseline in CDRS-R total score. The value is 1 for CDRS-R responders and 0 otherwise
- *CDRS-R remitters* are defined as patients with $CDRS-R \leq 28$. The value is 1 for CDRS-R remitters and 0 otherwise

The total score at a particular visit will be calculated using (sum of nonmissing items) \times (total number of items) / (number of nonmissing items) only if the number of missing items is ≤ 2 for the CDRS-R score.

If a patient misses a postbaseline visit or if his/her postbaseline visit is outside of the visit time window, a record for the scheduled visit will be imputed using the last observed nonmissing value immediately before the missing value. If the missing value occurs at Week 1, the baseline value will be carried forward for Week 1, provided that at least 1 subsequent postbaseline assessment is available. For a composite scale such as CDRS-R total score, individual items of the rating scale will not be carried forward. Only total scores will be carried forward using the LOCF approach.

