### **9.3 SELECTION OF STUDY POPULATION**

#### **9.3.1 Inclusion Criteria**

Patients must provide assent to participate and their LAR and caregiver (even if the same as the LAR) must provide written informed consent prior to the conduct of any study-specific procedures (see also [Section 5.3](#)).

To be eligible to participate in the study, patients must meet the following criteria:

1. Male or female outpatients between 12-17 years of age, inclusive, at Visit 1
2. Patients must meet DSM-IV-TR criteria for MDD, confirmed by K-SADS-PL
3. Patients must have a score  $\geq 40$  on the Children's Depression Rating Scale-Revised (CDRS-R) at Visits 1 and 2
4. Patients must have a Clinical Global Impressions-Severity (CGI-S) score  $\geq 4$  at Visits 1 and 2
5. Patients must have a caregiver who can and is willing to consent to be responsible for safety monitoring of the patient, provide information about the patient's condition, oversee the administration of investigational product, and accompany the patient to all study visits (see Section 5.3)
6. Patients must have normal physical examination findings, vital sign values, clinical laboratory test results, and electrocardiogram (ECG) results or abnormal results that are judged not clinically significant by the Investigator
7. Female patients must have a negative serum  $\beta$ -human chorionic gonadotropin ( $\beta$ -hCG) pregnancy test result at Visit 1

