##### ***9.5.1.1 Primary Efficacy Assessment***

The CDRS-R ([Appendix V](#); [Poznanski and Mokros, 1996](#)) is a semi-structured, clinician-rated instrument designed for use with children and adolescents between the ages of 6-17 years and contains 17 ordinaly-scaled items that evaluate the presence and severity of symptoms commonly associated with childhood depression. The CDRS-R total score ranges from 17 to 113.

The CDRS-R will be administered separately to the patient and to the caregiver. For each item, the clinician administering the interviews will select the rating that provides the best description of the patient and will then determine the total score.

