10.2 SECONDARY EFFICACY PARAMETER

The secondary efficacy parameter is the change from baseline to Week 8 in CGI-S score, which will be analyzed using the MMRM approach similar to the one used for the primary efficacy parameter. A sensitivity analysis will also be performed using the LOCF approach as described in Section 10.1.

[figure not shown]
To control the overall type I error rate for multiple comparisons across the primary and the secondary efficacy parameters and multiple doses, the matched parallel gatekeeping procedure (Chen et al., 2005) will be implemented. The primary hypotheses family, F_1 , consists of 2 null hypotheses H_{11} and H_{12} which are for comparisons of levomilnacipran 40 mg and 80 mg, respectively, with placebo in regard to the primary efficacy parameter, change from baseline to Week 8 in CDRS-R total score. Similarly for the secondary efficacy parameter, change from baseline to Week 8 in CGI-S score, we have the corresponding hypotheses family $F_2 = \{H_{21}, H_{22}\}$. Family F_1 will serve as the parallel gatekeeper for F_2 . Then the matched gatekeeper procedure utilizes the special logical relationship between the primary and the secondary parameters to enhance the power of statistical testing, i.e., primary and secondary hypotheses are matched on dose. The secondary efficacy parameter will be tested at a specific dose only if the corresponding primary efficacy parameter is statistically significant. Weighted Simes test will be performed to derive the local p-values for the intersection hypotheses. Assignment of weight for all $2^4 - 1 = 15$ intersection hypotheses is shown in Table 10.2–1.

[figure not shown]
Table 10.2–1. Weights for Intersection Tests in the Matched Parallel Gatekeeping Procedure

Intersection hypothesis	Weight			
	H_{11}	H_{12}	H_{21}	H_{22}
$H_{11} \cap H_{12} \cap H_{21} \cap H_{22}$	0.5	0.5	0	0
$H_{11} \cap H_{12} \cap H_{21}$	0.5	0.5	0	0
$H_{11} \cap H_{12} \cap H_{22}$	0.5	0.5	0	0
$H_{11} \cap H_{12}$	0.5	0.5	0	0
$H_{11} \cap H_{21} \cap H_{22}$	0.5	0	0	0.5
$H_{11} \cap H_{21}$	1	0	0	0
$H_{11} \cap H_{22}$	0.5	0	0	0.5
H_{11}	1	0	0	0
$H_{12} \cap H_{21} \cap H_{22}$	0	0.5	0.5	0

$H_{12} \cap H_{21}$	0	0.5	0.5	0
$H_{12} \cap H_{22}$	0	1	0	0
H_{12}	0	1	0	0
$H_{21} \cap H_{22}$	0	0	0.5	0.5
H_{21}	0	0	1	0
H_{22}	0	0	0	1

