Sample size recalculation based on interim analysis: following a blinded interim analysis, the sample size has been re-estimated. The MMRM model to estimate the pooled variance for change from baseline in CDRS-R total score at Week 8 includes pooled study site and week as factors and baseline CDRS-R total score and baseline value-by-week interaction as covariates, where week is included as a class variable. A total of 421 patients were included in the ITT analysis. Of these 421 patients, 347 (82.4%) patients have observed data at Week 8, so the estimated drop-out rate at Week 8 is 17.6%. Based on the MMRM model, the variance estimate for the change from baseline in CDRS-R total score at Week 8 is 129.53, and the estimated pooled standard deviation is 11.38. Thus the estimated effect size is 0.35 based on a treatment difference of 4 units and a pooled standard deviation of 11.38. Assuming an effect size of **0.35**, a common dropout rate of **17.6%**, and a correlation of 0.7 between the repeated measures, an estimated total sample size of **544** patients (**136** per treatment group) will be needed to maintain the 85% power to detect the treatment difference of 4 units for at least one levomilnacipran group versus placebo and for fluoxetine versus placebo.

15.0

STATISTICAL SOFTWARE

Statistical analyses will be performed using

[REDACTED]

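### Should CDRS-R response subtract the scale minimum of 17, given that a patient entering at 40 to 46 can be a remitter but not a responder?

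*SAP*

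**What the plan says.** SAP section 16.2 sets two binary variables. Responders are patients with a 40% or greater "reduction from baseline in CDRS-R total score. The value is 1 for CDRS-R responders and 0 otherwise". Remitters are patients scoring 28 or less, and "The value is 1 for CDRS-R remitters and 0 otherwise". The same section forms the total by summing the items, prorated when up to two are missing. No readable text subtracts the scale minimum before the percentage is taken.

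Protocol section 9.5.1.1 states: "The CDRS-R total score ranges from 17 to 113". Protocol section 9.3.1 requires a score of at least 40 on the "Depression Rating Scale-Revised (CDRS-R) at Visits 1 and 2", so baselines from 40 upwards are admitted.

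Neither variable is a confirmatory endpoint. The primary parameter is the Week 8 change in CDRS-R total score (SAP section 10.1), and "The secondary efficacy parameter is the change from baseline to Week 8 in CGI-S score" (SAP section 10.2). The four hypotheses in the gatekeeping procedure concern those two changes only. The readable text does not show how response and remission are analysed. The places where such analyses could stand are redacted or missing from the public copy, which is not a fault of the plan.

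**The concern.** A percentage reduction is easiest to interpret when zero means no symptoms. Here no symptoms means 17. Forty percent of the raw total is therefore a larger share of the possible improvement for a mild entrant than for a severe one, and the response rate mixes bars of different heights.

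The second oddity is more visible. Readers usually take response as the lower hurdle and remission as the higher one. At a baseline of 40, response requires a score of 24 or less, while remission requires only 28 or less, so the usual order reverses. Anyone who assumes that all remitters are responders would be wrong for some of the mildest patients.

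What is at stake is the meaning of a supportive rate. The obvious remedy would be a second response variable that measures reduction against baseline minus 17, with its own cut-off, fixed before unblinding so that it could not look data-driven.

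**Working it through.** The documents state no response or remission rate, so there is no plan figure to reproduce. The check has three parts.

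**1. Exact consequences of the rules.** Let B be baseline. The inputs are the 40% rule and the 28 cut-off (SAP 16.2), the minimum of 17 (Protocol 9.5.1.1) and entry at 40 or more (Protocol 9.3.1). The reduction required is 0.4B and the achievable reduction is B − 17. The share required is 0.4B/(B − 17), and the highest responding score is 0.6B.

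| Baseline | Reduction required | Achievable | Share | Highest responding score |
|---|---|---|---|---|
| 40 | 16 | 23 | 69.6% | 24 |
| 50 | 20 | 33 | 60.6% | 30 |
| 60 | 24 | 43 | 55.8% | 36 |
| 80 | 32 | 63 | 50.8% | 48 |

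A remitter can be a non-responder when 0.6B < 28, that is, when B < 28/0.6 = 46.7. With whole-number scores, the final scores that give remission without response are:

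- baseline 40 or 41: 25 to 28
- baseline 42 or 43: 26 to 28
- baseline 44: 27 or 28
- baseline 45 or 46: 28 only
- baseline 47 or more: none

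For example, 40 to 28 is a 12/40 = 30.0% reduction, 46 to 28 is 18/46 = 39.1%, and 47 to 28 is 19/47 = 40.4%.

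**2. How many patients.** The documents give no baseline distribution and no mean change, so these figures rest on assumptions:

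- baseline normal with mean 55 or 60 and SD 8 or 12, truncated at 40
- mean change −16, −20 or −24, independent of baseline
- SD of change 11.38, because in SAP section 14.0 "the estimated pooled standard deviation is 11.38"
- scores rounded and limited to 17–113

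That gives 12 scenarios, each simulated with 1,000,000 patients. Across them, 4% to 16% of patients enter at 40 to 46. Those who are remitters but not responders make up 0.22% to 1.29% of all patients: 0.0022 × 544 = 1.2 and 0.0129 × 544 = 7.0. Divided over four arms, that is about 0.3 to 1.8 patients per arm.

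If mean change is instead proportional to B − 17, the overall share stays at 0.2% to 1.3%. The share among remitters who entered at 40 to 46 does move, from 7–15% to 14–22%, so that subgroup figure should not be relied on. Also, 11.38 comes from a model adjusted for baseline and site, so it is a residual SD used here in place of the raw SD of change.

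**3. Would a floor-corrected rule be better?** Take response as (B − score)/(B − 17) at or above a cut-off c. Every eligible remitter responds if c is at most (40 − 28)/(40 − 17) = 12/23 = 52.2%, which points to 50% as a round value. Compared with the raw rule, under the assumptions in part 2:

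- Reported response rises by about 8 to 10 points.
- A responder can still score 40 or more, the entry threshold, from a baseline of 63 (0.5B + 8.5 = 40), against 66.7 under the raw rule (0.6B = 40). Such patients are 1.0% to 5.4% of the total, against 0.3% to 3.4%.
- Under the raw rule, entrants at 40 to 46 already respond more often than entrants at 60 or above: 45–72% against 16–44%, a gap of 25 to 34 points. The corrected rule widens the gap to 31 to 42 points.

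With change proportional to B − 17, the gap (mild minus severe) runs from −16 to +3 points under the raw rule and from −9 to +11 under the corrected rule. Correction shifts the gap in favour of mild entrants. It narrows the gap where severe entrants were well ahead and widens it where mild entrants were already ahead.

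**The case for a change.** The best case for a change is that two definitions in one section can give labels that look contradictory, that the affected baselines are expressly admitted, and that one supportive line fixed before unblinding would cost almost nothing while the 40% rule stayed for comparison with other trials. The varying bar also applies at every baseline, not only between 40 and 46.

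The facts in that case stand. The inference to a needed change does not. A patient who goes from 40 to 28 has had a 30% reduction and does score 28 or less, so both labels are true under rules that are fixed in advance and reproducible. The documents make no claim that remission lies inside response.

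The extra line is not free either. Its 50% cut-off would be chosen to produce the nesting, with no clinical basis in the documents. It would put a second, more favourable response rate beside the first, which invites selective citation. Its main purpose, a fairer bar across baseline severity, is not shown: it depends on how change relates to baseline, which the documents do not tell us.

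**Conclusion.** No change follows. The observation is correct: the share of achievable improvement needed for response falls from 70% at a baseline of 40 to 56% at 60, and remission without response is possible for baselines of 40 to 46. It identifies no error in a stated number and no fault in a primary or secondary test. All arms face the same rule, and no bias between arms has been shown. The size is small: about 0.2% to 1.3% of patients, or 1 to 7 of 544, on assumed baseline and change distributions, and that overall range held under both models of change.

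Percent of the raw total and percent of the achievable range are both defensible metrics. Replacing or doubling the first with the second exchanges one imperfection for another without a demonstrated gain. If the results tables show both rates, a footnote that remission does not imply response below a baseline of 46.7, or a cross-table of the two, would prevent misreading. That is presentation, and the plan does not need it to be sound.

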16.3 AGE-AND-GENDER-CORRELATED VALUES FOR WEIGHT AND HEIGHT

To adjust weight (kg) and height (cm) for sex and age, one needs to compare them to standard reference values for the same sex and age group, which are available in the United States Growth Charts and can be downloaded from:
http://www.cdc.gov/growthcharts/percentile_data_files.htm

The z-score is calculated as below

$$z = \frac{(X/M)^L - 1}{SL}, \text{ if } L \neq 0 \text{ and}$$

$$z = \frac{\ln(X/M)}{S}, \text{ if } L = 0,$$

where X is the physical measurement (eg weight and height) and L, M and S are the values from the appropriate table corresponding to the age in months (or length/stature) and sex (1 = male; 2 = female). X must be in metric measurements (kilograms or meters). This is called LMS method (Cole TJ, 1990), and parameters L, M, and S are the Box-Cox transformation power, median, and standard deviation, respectively, in the reference data, which again are provided in the reference data tables.

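### Could SAP 16.3 give wrong height z-scores by naming height in centimeters but the formula input in meters?

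*SAP*

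**What the plan says.** SAP 16.3 opens with "To adjust weight (kg) and height (cm) for sex and age", so weight is in kilograms and height in centimeters. It sends the reader to published growth-chart tables and gives the two branches of the LMS formula, one for L not equal to 0 and one for L = 0. The inputs are described in these words: "where X is the physical measurement (eg weight and height) and L, M and S are the values from the appropriate table", by age in months and sex. The unit rule follows: "X must be in metric measurements (kilograms or meters" (the bracket ends there). The section closes by saying that "parameters L, M, and S are the Box-Cox transformation power, median, and standard deviation, respectively, in the reference data". It states no unit for M and no conversion from centimeters to meters.

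No other visible section gives a height unit for this calculation. SAP 8.0 lists height among the baseline characteristics without a unit.

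**The concern.** The one sentence with a mandatory tone names meters for a length, while the section's first sentence has height in centimeters. At most one of these can match M. A programmer who took the rule literally, converted heights to meters and then divided by a median tabulated in centimeters would produce height z-scores with no meaning. So would one who left heights in centimeters against a median in meters. The condition that actually matters, that X and M share a unit, is never written down. What is at stake is the height z-score for every patient. Weight z-scores are not affected, because kilograms appear in both sentences.

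**Working it through.** **Inputs.** The formulas come from SAP 16.3: z = ((X/M)^L - 1)/(S·L) for L ≠ 0, and z = ln(X/M)/S for L = 0. The section states no numerical result, so there is no figure of the plan to reproduce. It also gives no L, M or S. The values below are assumptions: M = 160 cm = 1.60 m, L between -3 and 3, S between 0.03 and 0.10.

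**How S must be read.** The SAP calls S a standard deviation, but the formula works on X/M, so S has to be relative to the median. Suppose the standard deviation were 7 cm around 160 cm and L = 1. A patient at 167 cm should get z = 1. Entering S = 7 gives (167/160 - 1)/7 = 0.04375/7 = 0.006. Entering S = 7/160 = 0.04375 gives 0.04375/0.04375 = 1. The relative reading is the workable one and is used below.

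**Step 1: matched units.** Take a height of 170 cm.
- In centimeters: X/M = 170/160 = 1.0625.
- In meters: X/M = 1.70/1.60 = 1.0625.
- L = 1, S = 0.04: z = 0.0625/0.04 = 1.56 in both.
- L = 0, S = 0.04: z = ln(1.0625)/0.04 = 1.52 in both.

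The choice between centimeters and meters has no effect once X and M agree.

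**Step 2: mismatched units, patient at the median (true z = 0).** X in meters with M in centimeters gives X/M = 1.60/160 = 0.01. The reverse gives X/M = 160/1.60 = 100.

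| L | S | X in m, M in cm | X in cm, M in m |
|---|---|---|---|
| -1 | 0.04 | -2475 | +24.75 |
| 0 | 0.04 | -115.13 | +115.13 |
| 1 | 0.04 | -24.75 | +2475 |
| 1 | 0.05 | -19.80 | +1980 |
| 2 | 0.05 | -10.0 | +99,990 |

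For example, at L = 1 and S = 0.04: (0.01 - 1)/0.04 = -24.75.

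**Step 3: the mildest case in the assumed range.** With X/M = 0.01, |z| falls as L or S rises, so the minimum is at L = 3 and S = 0.10: (1 - 0.01^3)/(0.10 × 3) = 3.33. The reverse mismatch gives the same minimum at L = -3.

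**Step 4: would a mismatch be seen?** Take the 170 cm patient with X in meters and M in centimeters: X/M = 1.70/160 = 0.010625. At L = 1 and S = 0.04, z = (0.010625 - 1)/0.04 = -24.73, against -24.75 for the median patient. At L = 3 and S = 0.10 both are -3.33. So a mismatch in this direction shifts the values and also removes nearly all their spread. The reverse mismatch keeps a spread, but its smallest value for a median patient over L from -1 to 2 and S from 0.03 to 0.05 is still +19.8. Neither pattern could pass for real height data.

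**The case for a change.** A derivation rule should be executable as written, without relying on someone noticing bad output. Kilograms in the bracket is exactly the unit meant for weight, so a programmer has some reason to take meters just as literally for height. The visible text also cannot prove that the variable goes unused. Much of the safety analysis is not public, SAP Section 4 puts table and listing specifications in a separate document, and the protocol's literature list includes the LMS methods paper although no visible protocol section cites it.

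Part of this stands. The two height units do sit a few lines apart, the matching condition is unstated, and tidier wording would cost one sentence. But the objection shows a possible misreading, not a wrong result. The bracket can fairly be read as asking for metric rather than imperial values, in which case centimeters are allowed. If instead M is in meters, the rule is literally right and only a routine conversion goes unmentioned. The section also tells the analyst to compare the measurement with reference values from a named table, and such a comparison presupposes a common unit. Leaving the unit of M to that table is ordinary practice.

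**Conclusion.** The wording is inconsistent, but no change to the plan is needed. If the units were mismatched, X/M would be wrong by a factor of 100. A median patient's z would then be at least 3.33 in absolute value over assumed L from -3 to 3 and S up to 0.10, with S read as relative to the median. That consequence depends on the unit of M, which the documents do not give, and on an analyst forming the ratio without looking at the table that supplies M. The same table lookup that provides L, M and S settles the unit, and an error would be obvious in the first listing. No visible summary names the height z-score, and the CDRS-R and CGI-S analyses, the sample size and the gatekeeping procedure do not depend on it. This is a clerical slip, and rewording it would change no result.

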16.4 REPEATED OR UNSCHEDULED ASSESSMENTS OF SAFETY PARAMETERS

If a patient has repeated assessments before the date of first dose of double-blind investigational product, the results from the final nonmissing assessment made before the date of the first dose of double-blind investigational product will be used as baseline. If end-of-double-blind-treatment period assessments are repeated or if unscheduled visits occur, the last nonmissing postbaseline assessment during the double-blind treatment period will be used as the end-of-double-blind-treatment-period assessment for generating summary statistics. Likewise, if end of double-blind down-taper period assessments are repeated or if unscheduled visits occur, the last non-missing assessment during the double-blind down-taper period will be used as the end-of-double-blind-down-taper-period assessment for generating summary statistics. However, all postbaseline assessments will be used to determine PCS values for laboratory parameters, vital signs and ECG parameters, and to determine most severe suicidal ideation and most severe suicidal behavior from C-SSRS. All assessments will be presented in the data listings.

16.5 MISSING DATE OF THE LAST DOSE OF INVESTIGATIONAL PRODUCT

When the date of the last dose of investigational product in the study taken during the double-blind treatment period is missing for a patient in the Safety Population, all efforts should be made to obtain the date from the Investigator. If it is still missing after all efforts, then the last visit date will be used as the last dose date.

16.6 MISSING SEVERITY ASSESSMENT FOR ADVERSE EVENTS

If severity is missing for an AE that started before the date of the first dose of double-blind investigational product, an intensity of mild will be assigned. If severity is missing for an AE that started on or after the date of the first dose of double-blind investigational product, an intensity of severe will be assigned. The imputed values for severity assessment will be used for the incidence summary; the values will be shown as missing in the data listings.

